#### SECTION G: Recruitment and Informed Consent

1. Attach copies of all applicable recruitment materials:
 

Recruitment Scripts (what will be said to participants during recruitment)  
 Recruitment Emails  
 Cover Letters  
 Flyers  
 Advertisements  
 Other:
2. Who will recruit potential participants?  
**We have recruited Capital High School and Boise High School in the Boise School District by contacting the principal. Participants will be recruited through the high schools from 12th grade classes. Student participants' names will be obtained from the registrar's list of seniors, which have the names, street addresses, and current phone numbers for all students. This information can be obtained directly from the registrar's computer database. Recruitment letters to parents will be sent directly from the school.**
3. Describe how, when, and where individuals will be first contacted about their interest in participating in the study (e.g., face-to-face, email, flyers, advertisements, phone call, etc.).  
**A pre-notification letter will be sent by the school to parents early in the academic year. A second letter will be sent explaining the study, include the consent form and a project-addressed stamped envelope for return of the consent form. A reminder letter and consent form with project-addressed stamped envelope will be sent to parents who do not return the initial consent form. All letters will be sent to parents' permanent addresses, provided to us via the registrar's office. Additionally, letters with consent form with a project-addressed stamped envelope will be sent home with students.**

Students with parental consent will be invited to participate in the research study during class. Students will be given an assent form which will address the voluntary nature of participation, participants' rights, the risks of participation, the availability of referral options outside the study for help with alcohol use prevention or treatment, data retention and storage information, protections for and limits to confidentiality, a description of the interventions, and procedures for reporting complaints and/or adverse events to the investigators and to the University Human Subjects Review Committee. Participants will be given a copy of the consent document. Students who elect not to participate will be given an alternative academic activity to complete under the supervision of the teacher during the assessment and intervention class periods.

4. Are you are directly emailing or mailing participants?

NO  
 YES

If yes, how are you obtaining emails and/or mailing addresses?

Participants' parents will be mailed, although recruitment letters to parents will be sent directly from the school, not from Boise State. Student participants' names will be obtained from the registrar's list of seniors, which have the names, street addresses, and current phone numbers for all students. This information can be obtained directly from the registrar's computer database.

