The proposed study extends the literature by examining the eCHECKUP TO GO with high school seniors over a longer follow-up period, as well as examining mediators and moderators of intervention effects. All 12th grade students at the two participating school sites will be given the opportunity to participate in the study. All participants will complete an assessment packet containing questionnaires including demographic

information, the quantity and frequency of their drinking, beliefs about both the quantity and frequency of their peers' drinking, alcohol beliefs and expectancies, problems associated with drinking, personality characteristics, and future goals (see attachment 1). Classrooms within the high school schools will be randomly assigned to the following groups: eCHECKUP TO GO and control group.

What is your research question? State your hypothesis.

**The project is designed to evaluate the following hypothesis:** Participants in the eCHECKUP TO GO intervention condition will report a reduction in their quantity of alcohol consumption and alcohol-related consequences relative to those in the control group. We are also interested in mechanisms of change (e.g. changes in estimates of peer drinking and/or drinking expectancies) and if this program is more effective for some students than others (e.g. gender, baseline drinking status, social-emotional maturity, college-bound status).

What will you do with the results of your study (e.g. contributing to generalizable knowledge, publishing, sharing at conference, etc.)? If this project is only for internal evaluation or to complete a class assignment, IRB may not be required. Please contact the ORC for additional information.

**Results of this study will be presented at conferences via oral or poster presentations and through publication in peer-reviewed journals. In addition a project summary report will be sent to the participating schools and/or school district.**

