## SECTION F: Participant Population

1. Provide a description of the participant population you intend to recruit and collect data from. Describe the characteristics of the participant population such as gender, age ranges, ethnic background and health status, as applicable to the research.

**Participants (12th grade students; N = 1000) will be recruited from Capital High School and Boise High School in the Boise School District. All 12th grade students will be given the opportunity to participate in the study.**

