**We anticipate the student participants will be healthy.**

2. Will your research involve vulnerable populations, such as children or adolescents under the age of 18, pregnant women, prisoners or cognitively, economically, or educationally impaired participants?

NO  YES (indicate population): \_\_\_\_\_

If yes, describe additional safeguards planned to protect the rights and welfare of this population(s):

Student participants recruited to this research study will be approximately 1000 high school seniors (ages 16-18) from Capital High School and Boise High School in the Boise School District. Classrooms within the schools will be randomized to intervention or assessment-only control conditions. Participants will be recruited from classes. A letter will be sent by the schools to parents and their students prior to the study explaining the research. Parents will be asked to return consent forms using a self-addressed stamped postcard. Students will be invited to participate in the research study during class. Those students who decline participation will participate in an alternate academic activity under the supervision of the teacher. Consent procedures will be the same for minors and 18 year old students as the Boise School District requires parental consent for 18 year old students.

The surveys will ask student participants about their own alcohol use/non-use and any negative consequences, attitudes and beliefs about alcohol use, reasons for using alcohol use, norms for alcohol use, personality characteristics, future plans, and demographic information. Similar procedures have been used in previous research with 9th grade students and high school seniors without adverse incident. Psychological risks posed by the research are primarily related to the content of the assessment measures. Items include thoughts and feelings that may be private and personal behavior such as alcohol use. These questions may make participants uncomfortable, or be perceived as an intrusion on their privacy. Although it is important to consider these potential risks, and it is important to point out the potential for these risks, we have not observed any indications of these risks materializing in all of our previous research using procedures similar to those we will use in the proposed study.

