All data and other information in this study will be maintained confidentially, but data will not be anonymous due to the longitudinal nature of participation. In order to protect against risks posed by the potential loss of confidentiality, we will take the following steps: 1) participants will be assured that they are free to refrain from answering any questions they do not wish to answer; 2) all data will be identified only by a unique personal identifier (PIN), which will be randomly generated for study purposes; 3) a master list of names and code numbers will be stored in locked file cabinets under the supervision of the PI and will be available only to research staff on this project. Data will be retained on computers with restricted and password protected access, without links to the master code list. All data based on this research will be reported in aggregate form.

3. Will you be recruiting students from a class that you teach? (See IRB [guidelines](#) for using your own students.)
 

NO  YES

If yes, explain why this population is necessary to the study, and how you will ensure participants do not feel coerced to participate. Coercion is a significant concern.
4. Will you be recruiting employees who report to you?
 

NO  YES

If yes, explain why this population is necessary to the study, and how you will ensure participants do not feel coerced to participate. Coercion is a significant concern.
5. Indicate any exclusion criteria for participants.  
**There are no exclusion criteria for recruitment other than not meeting inclusion criteria other than not being a senior at one of the two school sites.**
6. How many participants do you anticipate are needed for this research?  
**We anticipate a 45% response rate (students with parental active consent, student assent, and who are present the day of data collection) - this will yield 450 student participants in this study which will provide a large enough sample to adequately power this study.**

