### *Statistical Analysis Plan*

To identify reductions in alcohol use and negative alcohol-related consequences among high school seniors over the duration of the study, we will evaluate each outcome using analysis of variance in a linear or generalized linear mixed model framework, with random effects of repeated observations on students, students nested in classes, periods or teachers, and within school. We will address the appropriateness of the model for non-normal outcomes and apply the appropriate distribution as necessary, and we will assess models for the necessity of all random effects using  $AIC_C$ . The fixed effects will include treatment (intervention, control), time (baseline, 6-weeks, and 6-months), and their interaction.

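### The SAP does not tie its cluster random effect to the randomised classroom, and the protocol does not state that each senior belongs to only one such classroom

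*Combined protocol and SAP*

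**What the plan says.** The unit of randomisation is given twice. Section E (Purpose): "Classrooms within the high school schools will be randomly assigned to the following groups: eCHECKUP TO GO and control group". Section F, item 2: "Classrooms within the schools will be randomized to intervention or assessment-only control conditions".

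Recruitment is described more loosely. Section F, item 1 says "All 12th grade students will be given the opportunity to participate in the study". Section G, item 2 says "Participants will be recruited through the high schools from 12th grade classes", and adds "Student participants' names will be obtained from the registrar's list of seniors". No course, class period or one-roster rule is named. Section H, item 4 has students in intervention classrooms take the online program in class time, so classroom membership determines exposure.

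The Statistical Analysis Plan specifies a linear or generalized linear mixed model with random effects for repeated observations on students and for "students nested in classes, periods or teachers, and within school". The need for every random effect is to be judged by AICc. The fixed effects are arm, time point and their interaction.

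The number of classrooms, the allocation ratio and the method of randomisation are not stated.

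**The concern.** In a cluster-randomised trial, the standard error of the treatment contrast has to reflect variation between the units that were randomised. The SAP names the classroom as only one of three possible grouping levels, and then lets a fit criterion remove it. If one teacher takes classes in both arms, or one period holds classes of both arms, a teacher or period effect leaves the variation between classrooms inside that group in the residual. The residual treats students as independent, so the standard error will tend to be too small and the evidence for the intervention overstated.

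The second gap concerns assignment. Nested random effects presume one group per student, and so does a classroom-delivered intervention. If a senior did appear on two randomised rosters, the plan gives no rule for that student's arm. Either someone would choose it afterwards, or a student who took the program could be counted as a control.

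**Working it through.** **The plan's own figure.** Section F, item 1: "Participants (12th grade students; N = 1000) will be recruited from Capital High School and Boise High School in the Boise School District". Section F, item 6: "We anticipate a 45% response rate". 1000 × 0.45 = 450, which is the stated yield. The accompanying claim of adequate power cannot be reproduced: no alpha, effect size, SD, intraclass correlation (ICC), number of classes or target power is given.

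**Randomised unit against analysis unit.**
- Randomised: the classroom (Sections E and F).
- Modelled: class, or period, or teacher (SAP), each subject to removal by AICc.
- If the class effect is fitted and kept, the two agree.
- If a teacher or period effect is fitted and its classrooms are split between arms, the two do not agree.
- If AICc drops the effect, no term represents the randomised unit.

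The SAP permits all three outcomes.

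**How much this could matter (illustration).** Assume k = 10 to 40 classrooms and ICC = 0.01 to 0.10; neither is in the documents. With m = 450/k participants per classroom, the variance of a between-arm comparison at one time point is inflated by 1 + (m − 1) × ICC.
- k = 40, ICC 0.01: m = 11.25; 1 + 10.25 × 0.01 = 1.10; true SE is √1.10 = 1.05 times one that ignores classrooms.
- k = 20, ICC 0.05: m = 22.5; 1 + 21.5 × 0.05 = 2.08; √2.08 = 1.44 times.
- k = 10, ICC 0.10: m = 45; 1 + 44 × 0.10 = 5.40; √5.40 = 2.32 times.

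These describe complete omission of classroom variation, so they bound the problem; a teacher or period effect may absorb part of it. For the treatment-by-time contrast, a classroom difference that is constant over time largely cancels. The ICC that matters there is that of the change, which is also not given and may be smaller.

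**A senior on two rosters (conditional).** Suppose k classes are split equally between arms. Given the arm of the first class, k/2 of the remaining k − 1 classes are in the other arm, so P(opposite arms) = (k/2)/(k − 1).
- k = 40: 20/39 = 51%.
- k = 20: 10/19 = 53%.
- k = 10: 5/9 = 56%.

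If classes are randomised separately by school and both rosters are in one school, k is that school's count. The result barely depends on k. It applies only to a student on two randomised rosters; with one roster per senior the probability is 0.

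**The case against.** A reader might infer that the SAP leaves the unit of randomisation open. It does not. The phrase concerns random effects in the model, and two sections name the classroom as the randomised unit. It is also possible that class, period and teacher are loose labels for the same section of students. If so, one sentence settles it, but the text as written does not say so.

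A reader might infer that students will sit in both arms. No passage shows this. The recruited classes could all be sections of one course that each senior takes once, and the SAP's nesting presupposes one group per student. Each participant also has a single code held against a master list until the 6-month data are in (Section I, item 1), so a duplicate could be detected. Later section changes have little force as a source of contamination: Section H, item 4 describes only surveys at 6 weeks and 6 months, not further intervention.

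A reader might also infer that a small number of classes, randomised without restriction, will leave the arms unlike. Neither premise is in the documents. The class count and method are unstated, randomising within the schools may already mean separately by school, and baseline is a time point in the model, so a stable baseline difference does not enter the interaction contrast.

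These objections remove the stronger readings. They do not answer the narrower one: nothing in the SAP guarantees that the randomised classroom is in the final model.

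**Conclusion.** The point holds in a limited form. The SAP as written permits clustering on a unit that was not randomised, or no cluster term at all, so the standard error of the treatment-by-time effect could be wrong, most likely too small. The documents do not allow its size to be fixed. Under the assumed class counts and ICCs, ignoring classrooms completely would understate the SE of a single-time comparison by a factor of 1.05 to 2.32. The effect on the change contrast depends on how far classrooms differ in change.

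The absence of a one-roster statement is a secondary gap in detail. The probability of roughly one half is conditional on dual membership, which is an open possibility and not a documented event. No claim of imbalance between arms is supported.

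**What to change.** **Statistical Analysis Plan.** Replace the three alternatives with the classroom as randomised, and keep that random effect whatever AICc shows. AICc may still be used for other random effects.

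**Sections E and F (item 2).** State that each senior is assigned to one randomised classroom from the roster at randomisation, and is analysed in that classroom and arm whatever later section changes occur. State that classrooms are randomised 1:1 within school.

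**Cost.** Minor wording, a roster fixed before the first session, and possibly a slightly larger standard error than a model with the classroom effect removed would report.

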#### RECRUITING BOISE STATE STUDENTS

Recruiting Boise State students may require additional internal and departmental permissions, in addition to IRB approval. It is the PIs responsibility to obtain these permissions before moving forward with recruitment. The Boise State Office of the Vice President for Student Affairs (VPSA) provides [guidelines](#) for sending mass emails to students. It is the PI's responsibility to be familiar with these guidelines and any additional departmental, college or unit processes.

5. Are you recruiting Boise State students?

NO, skip to #6  
 YES:

Indicate which students or employees you are targeting:

Approval(s) obtained and attached, if applicable.

6. *Attach copies of all applicable informed consent materials:*

Informed Consent Form  
 Cover Letter  
 Web-based Cover Letter  
 Assent Form  
 Parent/Guardian Informed Consent Form  
 Verbal Consent Script  
 Debriefing Statement

7. Are you requesting an alteration or waiver to any informed consent requirements, including documentation of informed consent (signed consent)?

NO  YES

If YES, complete the section below. If NO, skip to question 4.

#### INDICATE THE TYPE OF WAIVER YOU ARE REQUESTING:

I am requesting to waive the required documentation of informed consent (i.e. waive obtaining the signature for anonymous internet-based survey, telephone survey, mailed survey, etc.). →COMPLETE SECTION A

I am requesting to waive or alter the required elements of the informed consent process.→COMPLETE SECTION B

#### SECTION A

Check the box next to the condition that best fits your research study and justify how your research study meets that condition. If waiving the signature, you must still submit a verbal script or cover letter for participants that addresses the eight required elements of consent as stated in 45 CFR 46.116 (a)(1-8).

CONDITION 1

The only record linking the participant and the research would be the consent document and the principal risk would be potential harm resulting from a breach of confidentiality. Each participant will be asked whether the participant wants documentation linking the participant with the research, and the participant's wishes will govern.

*Justify why your study meets this condition:*

**CONDITION 2**

The research presents no more than minimal risk to the participant and involves no procedures for which written consent is normally required outside the research context (i.e. no questions are being asked that could result in potential embarrassment, personally or professionally.)

*Justify why your study meets this condition:*

**SECTION B**

I am requesting to **waive the informed consent process**.

I am requesting **alteration** of the informed consent process.

*Describe which elements of consent will be altered and/or omitted:*

You must justify your request to waive or alter the informed consent process in accordance with each of the following four criteria established under 45 CFR 46.116 (d) (1-4). Provide supporting information for **ALL FOUR** criterion:

1. The research involves no more than minimal risk to the participants.

*Justify:*

2. The waiver or alteration will not adversely affect the rights and welfare of the participants.

*Justify:*

3. The research could not practicably be carried out without the waiver or alteration.

*Justify:*

4. Whenever appropriate, the participants will be provided with additional pertinent information after participation. (*If a debriefing statement is used, submit a copy with this application.*)

*Explain:*

8. Describe the **consent process**. Do not answer, "see attached consent form," as this does not describe the **process** of obtaining informed consent. **Describe how, when and where the informed consent process will take place and who will obtain informed consent.**

**A pre-notification letter will be sent by the school to parents early in the academic year. A second letter will be sent explaining the study, include the consent form and a project-addressed stamped envelope for return of the consent form. A reminder letter and consent form with project-addressed stamped envelope will be sent to parents who do not return the initial consent form. All letters will be sent to parents' permanent addresses, provided to us via the registrar's office. Additionally, letters with consent form with a project-addressed stamped envelope will be sent home with students.**

9. If the participants are not able to give legal consent (e.g., minors), explain how assent will be secured.

**Students will be invited to participate in the research study during class. Students will be given an assent form which will address the voluntary nature of participation, participants' rights, the risks of participation, the availability of referral options outside the study for help with alcohol use prevention or treatment, data retention and storage information, protections for and limits to confidentiality, a description of the interventions, and procedures for reporting complaints and/or adverse events to the investigators and to the University Human Subjects Review Committee. This will be presented by [name]. It will be clearly stated to the participants that participation is voluntary. Students who elect not to participate will be given an alternative activity to complete during the assessment and intervention class periods.**

10. Into what languages will the consent be translated? (*NOTE: Translated consent documents must be reviewed and approved by the IRB prior to use.*)

